## 5.10 Supply, Packaging, Labelling and Storage

IMPs are KY1044 and atezolizumab, both of which will be provided by the Sponsor to the investigational site as open-label liquid solutions in vials.

KY1044 drug substance has been manufactured in accordance with current Good Manufacturing Practice (GMP) at Lonza Biologics plc, Slough, UK, and subsequently KY1044 drug product has been manufactured by Nova Laboratories Ltd, Leicester, UK.

Atezolizumab drug product has been manufactured in accordance with current GMP and supplied by F Hoffman-La Roche.

Both IMPs (KY1044 and atezolizumab) will be labelled, packaged and distributed by PCI Clinical Services. Labelling will be done in accordance with GMP guidelines and regulatory requirements of each country participating in the study. Investigational sites will supply all ancillary supplies as detailed in the pharmacy manual, including all materials required for the preparation and administration of KY1044 and atezolizumab doses.

Property of the Sanofi Group - strictly confidential

After release procedures have been completed in accordance with regulatory requirements and as needed thereafter, IMPs will be shipped with temperature monitoring devices to the responsible person at the investigational site pharmacy.

IMP delivered to sites, and prepared doses, must be maintained at 2 to 8°C and stored in a secure environment ie, with restricted access, and in accordance with any locally applicable regulations. Before administration, prepared doses of the IMP need to be brought to room temperature at least 1 hour before administration.

Details of procedures for the receipt, storage, and management of IMP supplies are provided in the Pharmacy Manual.

### 5.11 IMP Accountability Records

The Investigator is responsible for accountability of all used and unused supplies of KY1044 and atezolizumab at the site.

IMP accountability forms will be completed by the Investigator and filed in the Investigator Site File (ISF). The IMP accountability forms will be kept current and will contain the dates and quantities of drugs received at site, and details of disposition of all drug received and preparation of individual doses.

At the end of the study, a final IMP reconciliation statement must be completed by the Investigator and provided to the Sponsor.

All IMP accountability forms must be made available for inspection by the clinical monitor, the Sponsor or representatives of the Sponsor, and regulatory agency inspectors.

At the end of the study, or at intervals confirmed by the Sponsor, and after the accountability has been verified, all IMP supplies including unused, partially used, or empty containers, will be destroyed locally according to the site requirements and local regulations or returned as directed by the Sponsor. Proof of delivery, certificates of destruction and/or IMP return documentation will be filed in the eTMF.

### 5.12 Procedures for Monitoring Patient Compliance

The Investigator or designee is responsible for the administration of the IMPs. The monitor will assess compliance throughout the study by reviewing drug reconciliation/accountability records on a periodic basis as outlined in the monitoring plan and guidelines.

### **6 STUDY ASSESSMENTS**

The schedule of procedures and assessments during the study is summarized and presented in Table 6-1 (Phase 1) and Table 6-2 (Phase 2).

10-Nov-2021 Version number: 1

#### Table 6-1:Phase 1 Assessments

Visit name	Screening	Cyc (21 We	cle 1 days; ek 1-3	study 3)	v Day 1	1-21;		Cyc (21 Day We	cle 2 days; s y 22-42; ek 4-6)	tudy		Cyc (21 Day	:le 3 days; 743-6	; study i3; W	eek 7-	9)	Cycle (21 da all Cy to 48 (4 yea	4 ays) and vcles up months urs)	EOT v (up to 21 days after the last study dose)	Safety follow-up visit (90 days after the last study dose)
Day of cycle	-28 to -1		CIDI	C1D2	C1D8	C1D11	C1D15		C2D1	C2D8	C2D15	LUE J	1000	C3D8	C3D11	C3D15	C4D1 and	CXD1		
		pre-dose	post-dose					pre-dose	post-dose			pre-dose	post-dose				pre-dose	post-dose		
Obtain Informed Consent	х																			
Obtain pharmacogenomic informed consent	x																			
Hospital admission a		х																		
IXRS	х	Xp						Хp				Хp					Xp		Х	
Demography	х																			
Inclusion/ exclusion criteria	х	Х																		
Medical History e	х																			
Height	х																			
Weight	х	х						х				х					х		х	
Physical examination d	х	х						х				х					х		х	
Vital signs e	х	х	х	х				x	х			х					х		х	
ECOG performance	х	Х						x				х					х		х	
Oxygen saturation test	х																			

Property of the Sanofi Group - strictly confidential

PAGE 92 OF 217

### Amended Clinical Trial Protocol 07

KY1044/SAR445256-KY1044-CT01/TCD17370 - alomfilimab

10-Nov-2021 Version number: 1

Visit name	Screening	Cyc (21 We	cle 1 days; ek 1-3	study 3)	v Day I	1-21;		Cyc (21 Day We	cle 2 days; s y 22-42 ek 4-6)	tudy ;		Cyc (21 Day	cle 3 days y 43-6	; study 53; W	eek 7-	9)	Cycle (21 da all Cy to 48 (4 yea	e 4 ays) and vcles up months urs)	EOT v (up to 21 days after the last study dose)	Safety follow-up visit (90 days after the last study dose)
Day of cycle	-28 to -1			C1D2	C1D8	CIDII	CID15		C2D1	C2D8	C2D15		CODI	C3D8	C3D11	C3D15	C4D1 and CXD1			
		pre-dose	post-dose					pre-dose	post-dose			pre-dose	post-dose				pre-dose	post-dose		
Cardiac markers f	x																			
12-Lead ECG g	x	х	х									х	x						х	
Review AE	x	х	х	x	х	х	x	х	х	х	х	х	x	Х	х	х	х	Х	x	х
Review Concomitant Medications	х	х						Х				х					х		x	х
Hematology	х	X h		X h	X h		X h	X h		X h	X h	X h		X h			X h		х	
Clinical Chemistry	х	X h			X h		$\mathbf{X}^{\mathbf{h}}$	X h		X h	X h	$\mathbf{X}^{\mathbf{h}}$		X h			X h		х	
Fasting lipid profile i	x																			
Coagulation (aPTT, INR)	х	X h						X h				X h					X h		х	
HbA1c j	х																		х	
Urinalysis	х	х						х				х					х		х	
Pregnancy test k	х	х						х				х					х		x	
Thyroid function 	х											х							х	
Viral testing, HIV, HBV, HCV m	х																			
Auto-Abs n	х							х									х		х	
Anti-KY1044 and Anti-atezolizumab (ADA)°		x						x				x					x			x

Property of the Sanofi Group - strictly confidential

PAGE 93 OF 217

### Amended Clinical Trial Protocol 07

KY1044/SAR445256-KY1044-CT01/TCD17370 - alomfilimab

10-Nov-2021 Version number: 1

Visit name	Screening	Cyc (21 We	cle 1 days; ek 1-3	study 3)	v Day :	1-21;		Cyc (21 Day We	cle 2 days; s v 22-42; ek 4-6)	tudy ;		Cyc (21 Day	cle 3 days: y 43-6	; study 53; W	y eek 7-	-9)	Cycle (21 da all Cy to 48 (4 yea	e 4 ays) and ycles up months ars)	EOT v (up to 21 days after the last study dose)	Safety follow-up visit (90 days after the last study dose)
Day of cycle	-28 to -1		CIDI	C1D2	C1D8	CID11	CID15		C2D1	C2D8	C2D15	Cabi		C3D8	C3D11	C3D15	C4D1 and	CXDI		
		pre-dose	post-dose					pre-dose	post-dose			pre-dose	post-dose				pre-dose	post-dose		
PK (KY1044) p		х	x	х	х	х	х	х	х			х	х	х	х	х	х	Х	Х	Х
PK (atezolizumab) p		Х	x					х	х			х	х				х	Х	Х	х
RNA signature from PBMC (Nanostring)		x			x			x		x										
Fresh tumor biopsy 	x									х										
PBMC FACS or ChipCytometry analysis		x			x			x		x										
ICOS Receptor Occupancy (PBMC) r		x			x			x		x										
Plasma cytokine /chemokine panel		х		x	х			x	X٩	Х		х	x	х						
Serological tumor markers t	x	х						х				x					х		Х	
Tumor Imaging RECIST 1.1 u	x													х						
KY1044 administration w		х						x				x					х			
Atezolizumab administration (only for patients on combination therapy)		x						x				x					x			

Property of the Sanofi Group - strictly confidential

PAGE 94 OF 217

Amended Clinical Trial Protocol 07 KY1044/SAR445256-KY1044-CT01/TCD17370 - alomfilimab 10-Nov-2021 Version number: 1

A window of 3 days is permissible to complete Day 1 assessments, a window of 1 day is permissible to complete all other assessments

- a After receiving the first infusion in Phase 1, patients will be either hospitalized or remain in the clinic for at least 6 to 8 hours until the last assessments. They will be provided with instructions for after hour care as per institutional standard and will return to the clinic on C1D2. Patients should remain in the clinic for at least 3 hours at all other visits where infusions are given.
- b IXRS contact can be performed prior to the patient's CXD1 visit to receive treatment allocation.
- c Medical History including date of diagnosis and dates and extent of cancer, prior antineoplastic therapies (chemotherapies, targeted agents, radiation, surgery) and current concomitant medication (including SARS-CoV-2 vaccines).
- *d* Complete physical examination should be performed at screening and at the EOT. This should also include a full dermatological examination (complete skin and mucosal exam). Abbreviated physical examination will be performed every cycle (see Section 6.5.2).
- e Vital signs: during Cycles 1 and 2, blood pressure (BP) and HR will be monitored in the clinic every 15 minutes during the infusions of study treatment and every 30 minutes inbetween the infusions (for combination therapy) and 60 min after the last infusion of study treatment and before the patients are discharged from the hospital on Cycle 1 Day 2. See Section 6.5.7.
- f Cardiac markers at screening will include: Baseline Troponin I for all patients. Additionally, N-terminal pro B-type natriuretic peptide (NT-pro-BNP) will only be taken for patients with a history of cardiac disease (according to exclusion criteria). Repeated assessments of cardiac markers during the study will be performed only when clinically indicated .
- g ECGs will be taken pre- and post-dose at Cycles 1, 3 and 6 as close as possible to the relevant PK timepoints (see Section 6.5.8). In the event of abnormal ECG findings and if clinically indicated, an unscheduled PK sample should be collected and Troponin I, together with assessments for CK, CK-MB, AST and lactate dehydrogenase (LDH). NT-pro-BNP should be measured together with the other cardiac markers as outlined above only in patients with previous cardiac complications at screening.
- h All samples will be analyzed centrally. On the occasions marked h only, duplicate samples for immediate access to key safety laboratory parameters (hematology, clinical chemistry and coagulation) will be analyzed at local labs as well.
- *i* At screening, clinical chemistry includes collection of a fasting lipid profile sample.
- j HbA1c should be measured every 12 weeks throughout the study and will be assessed at EOT only if the previous assessment has not been performed within the last 3 months.
- k Serum pregnancy test ( $\beta$ -HCG) will be performed at screening. Urine dipstick test will be performed at all other visits.
- 1 Thyroid function includes free T4 and TSH and the analyses will be repeated every 3 cycles and at EOT.
- *m* Virology testing will be performed at screening for HIV, HBV and HCV. In patients, who are known to be positive for HBV and HCV, tests will be repeated every cycle pre-dose and a confirmatory sample should be taken when clinically indicated. See Section 6.5.9 for more details.
- *n* Auto-antibodies include: anti-DNA, anti-nuclear, anti-mitochondrial and anti-phospholipid antibodies and Rheumatoid factor (RF) and acetyl-choline receptor antibodies (AChR). When a blood sample is positive for ANA (ie, titer >40) it will be tested for antibodies against extractable nuclear antigens. Samples for auto-antibody analyses will be collected at screening, every second cycle pre-dose for the first six cycles (C2, C4, C6), then every 12 weeks up to 48 months of treatment, when clinically indicated and at EOT.
- 0 ADA samples should be collected at every cycle at pre-dose on Day 1 and unscheduled at any time, when clinically indicated. For detailed ADA sample collection schedule see Section 6.4.2.
- p PK samples will be taken pre- and post-dose during all cycles and unscheduled at any time, when clinically indicated. For detailed PK analysis timings please refer to Section 6.4.2. Note: On days and timepoints when biomarker and pharmacokinetic blood samples are being collected, the PK sample must be drawn first. For further details please see schedule
- of PK assessments in Section 6.4.2 and biomarker assessments in Section 6.3.1.
   q In patients with measurable disease, a fresh tumor biopsy should be taken once other screening investigations strongly suggest the patient is likely to be eligible, to avoid unnecessary risk of biopsy for a patient who is not going to be eligible. Where a prior (archival) biopsy is available that is less than 3 months old this may be substituted for a fresh tumor biopsy at screening. A
- fresh tumor biopsy is mandatory on treatment (C2D8). Where feasible, collection of a tumor biopsy at progression is encouraged. *r* Samples for the analysis of ICOS Receptor Occupancy will be collected from patients on KY1044 single agent only.
- Samples for the analysis of ICOS Receptor Occupancy will be collected from patients on KY 1044 single agent only.
- s Plasma sample for cytokine analysis post dose timepoint is 6 to 8 hours post-infusion on C2D1 and C3D1. Unscheduled sample may be collected if required.
- t Blood sample for measurement of serological tumor markers will be taken at screening, pre-dose of every cycle and EOT only for those patients that have tumors with correlative serological markers.
- u Tumor Imaging RECIST 1.1 assessment is done every 8 weeks ( $\pm$ 7 days) after the start of treatment for the first 16 weeks, after that every 12 weeks ( $\pm$ 7 days) for 48 months of treatment duration or until objective disease progression; visit window for assessment is  $\pm$ 7 days. In case of progression of disease without clear clinical signs of progression, the patient should continue

Property of the Sanofi Group - strictly confidential

PAGE 95 OF 217

Amended Clinical Trial Protocol 07 KY1044/SAR445256-KY1044-CT01/TCD17370 - alomfilimab 10-Nov-2021 Version number: 1

treatment. In this case a confirmatory scan should be scheduled 4 to 8 weeks later as per iRECIST guidelines. The thorax CT/ magnetic resonance imaging (MRI) scan performed at screening as part of the RECIST assessment will document the lung parenchyma status.

- *v* Please see Section 8.1 for details of follow up after end of treatment visit.
- W KY1044 is always to be administered first followed by a saline solution flush to empty the line as described in the pharmacy manual. For the combination part, a slow saline infusion will continue (after this saline flush) for approximately 1 hour before starting the atezolizumab infusion at the same infusion site. There should be a period of at least 1 hour after the infusion(s) is complete whereby the patient requires close observation as outlined in Section 5.2.2.

Amended Clinical Trial Protocol 07 KY1044/SAR445256-KY1044-CT01/TCD17370 - alomfilimab 10-Nov-2021 Version number: 1

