ICOS is expressed on different CD4 T cell subsets. Although blockage of CTLA-4 with ipilimumab has been shown to induce ICOS expression on Th1 CD4 T cells which is associated with a higher response rate in treated patients (15), it was previously reported that ICOS is expressed more on the surface of Th2 cells (which are IL-4 and IL-10 producing cells) rather than on Th1 cells (which produce IFN $\gamma$ ) (12). Similarly, murine ICOS+ CD4 TRegs are characterized by superior survival and highly suppressive properties compared with ICOS TRegs (8). Altogether, these data demonstrate that ICOS is preferentially expressed on the surface of pro-tumorigenic T cells.

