- 14. Warfarin and other types of long acting anticoagulants (such as phenprocumon and or anti-Xa inhibitors with a half-life of >12 hours) is prohibited within 4 weeks of the first dose of study treatment and patients requiring anticoagulant treatment should switch to low molecular weight heparin or anti-Xa inhibitors with a half-life of ≤12 hours
- 15. Use of live or live attenuated vaccines against infectious diseases (examples include, but are not limited to, intranasal influenza, measles, mumps, rubella, oral polio, Bacillus Calmette-Guérin vaccine, rotavirus, varicella, yellow fever, TY21a typhoid vaccines etc) within 4 weeks of the first dose of study treatment and it should not be planned to administer such a vaccine during the course of the study. SARS-CoV-2 vaccines authorized for use by the competent local regulatory health authorities for active

immunization to prevent COVID-19 are allowed (unless the vaccine is live or live attenuated) and must be given in accordance with the prevailing immunization guidelines. SARS-CoV-2 vaccination may be given at least 7 days prior to the planned first dose of study treatment. Refer to Table 5-6 for more instruction with regard to SARS-CoV-2 vaccination.

- 16. Systemic anti-cancer therapy (TKI and/or chemotherapy) within 2 weeks of the first dose of study treatment. For cytotoxic agents that have major delayed toxicity, eg, mitomycin C and nitrosoureas, 4 weeks is indicated as washout period
- 17. Major surgery within 2 weeks of the first dose of study treatment (mediastinoscopy, insertion of a central venous access device, and insertion of a feeding tube are not considered major surgery)
- 18. Anti-CTLA4, anti-PD-(L)1 treatment within 4 weeks of the first dose of study treatment
- 19. Pre-treatment with anti-CTLA4 antibodies in combination with any other antibody or drug specifically targeting T-cell co-stimulation or checkpoint pathway
- 20. Participation in an interventional, investigational study within 4 weeks of the first dose of study treatment
- 21. Presence of CTCAE v5 ≥Grade 2 toxicity (except alopecia, peripheral neuropathy and ototoxicity, which are excluded if CTCAE v5 ≥Grade 3) due to prior cancer therapy

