- *n* Auto-antibodies include: anti-DNA, anti-nuclear, anti-mitochondrial and anti-phospholipid antibodies and Rheumatoid factor (RF) and acetyl-choline receptor antibodies (AChR). When a blood sample is positive for ANA (ie, titer>40) it will be tested for antibodies against extractable nuclear antigens. Samples for auto-antibody analyses will be collected at screening, every second cycle pre-dose for the first six cycles (C2, C4, C6), at EOT and then every 12 weeks up to 48 months of treatment and when clinically indicated.
- 0 ADA samples should be collected at every cycle on Day 1 and unscheduled at any time, when clinically indicated. For detailed ADA sample collection schedule see Section 6.4.2.
- p PK samples will be taken pre- and post-dose during all cycles and unscheduled at any time, when clinically indicated. For detailed PK analysis timings please refer to Section 6.4.2. Note: On days and timepoints when biomarker and pharmacokinetic blood samples are being collected, the PK sample must be drawn first. For further details please see schedule of PK assessments in Section 6.4.2.
- *q* Fresh tumor biopsy should be taken once other screening investigations strongly suggest the patient is likely to be eligible to avoid unnecessary risk of biopsy for a patient who is not going to be eligible. Where a prior (archival) biopsy is available no older than 3 months, the archival tissue may be substituted for a fresh tumor biopsy at screening. A fresh tumor biopsy is mandatory on treatment (C2D8). Where feasible, collection of a tumor biopsy at progression is encouraged.
- r Plasma sample for cytokine analysis post dose timepoint is 6 to 8 hours post-infusion on C1D1 and C2D1 and C3D1. Unscheduled sample may be collected if required.
- s Blood sample for measurement of serological tumor markers will be taken at screening, pre-dose of every cycle and EOT only for those patients that have tumors with correlative serological markers.

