### 6.3 Assessment of Pharmacodynamics

### 6.3.1 Biomarkers

Biological samples (eg, archived and fresh tumor samples or blood samples) will be collected and may be analyzed for exploratory predictive or responsive biomarkers (see Section 6.3.2 and Section 6.3.3).

There is a high need to identify and validate biomarkers with the aim of selecting indications and patients who will best respond to KY1044 as single agent and/or to the combination with atezolizumab and also to correlate the PD effects of the treatments with clinical outcomes such as efficacy and toxicity. Such biomarkers will be explored at the soluble (plasma), cellular, and transcriptomic levels.

In addition, it is proposed to use PD readouts to contribute to the process of RP2D decision. These biomarkers/PD markers include immune cell profiling (to be analyzed by RNA and/or Protein) in the blood and in the TME ( $T_{Regs}$  quantification, ICOS expression, number of CD8, TILs contents) pre and post treatment. Diagnostic and prognostic gene signatures derived from pre-clinical *in vitro* and *in vivo* models will also be examined using relevant patient samples (PBMC and Tumor) where appropriate consent has been provided.

Finally, cytokines such as IFN $\gamma$ , TNF $\alpha$  and GM-CSF will be assessed in the plasma of the patients.

Alternative biomarkers may be evaluated as determined by additional data associated with safety, disease progression or response to KY1044 as single agent or in combination with atezolizumab. The results obtained from this study may be pooled with biomarker data from other studies to test existing hypotheses or to generate hypotheses to be tested in future studies where KY1044 may be combined with other agents. A summary of the biomarker samples is provided in Table 6-4.

Table 6-4:	Biomarker	Sample	Collection	Plan	(Tumor/Blood	Samples)	for
	Phase 1 and	2					

Sample type	Visit/ Timepoint a	Approx. volume (blood samples)	Marker b	Purpose
Tumor samples c				
Newly obtained tumor sample	Screening and during treatment C2D8	N/A	IHC expression of markers such as: ICOS, CD8, FOXP3 (secondary endpoint) and other markers such as CD163, CD68, PD-L1 etc. (exploratory endpoint)	Assess expression status of potential predictors of efficacy. PD markers
			Transcriptomic analysis of immune-related genes (exploratory endpoint)	

Sample type	Visit/ Timepoint a	Approx. volume (blood samples)	Marker b	Purpose

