			Analysis of pharmacogenomics markers	
Blood samples				
Blood sample (Plasma) for cytokine analysis b	C1D1 (pre-infusion) C1D2, C1D8, C2D1 (pre-infusion), C2D1 (6-8 hours post-infusion), C2D8 C3D1(pre-infusion), C3D1 (6-8 hours post- infusion),C3D8 and unscheduled d	1 x 5 mL of blood per timepoint	Cytokine analysis (eg, IFNγ, TNFα, GM-CSF) (exploratory endpoint)	PD effect
Blood sample (PBMC) for Immunoprofilling	C1D1 (pre-infusion), C1D8, C2D1 (pre-infusion), C2D8 and unscheduled	1 x 4 mL of blood per timepoint	Phenotypic characterization of circulating ICs by FACS/ChipCytometry (eg, CD8, CD4, T Regs and B cells) (exploratory endpoint)	PD effect
Blood sample (PBMC) for pharmacogenomics testing	C1D1 (pre-infusion), C1D8, C2D1 (pre-infusion), C2D8 and unscheduled	1 x 8 mL of blood per timepoint	Transcriptomic analysis of PBMC using customized IO360 panel from Nanostring (exploratory endpoint) Analysis of	PD effect Samples will be taken only if PGx ICF is signed
			pharmacogenomics markers	
Blood Samples (PBMC) for receptor occupancy (KY1044 single agent in Phase 1 only)	C1D1 (pre-infusion), C1D8, C2D1 (pre-infusion), C2D8 and unscheduled	1 x 8 mL of blood per timepoint	KY1044 binding to CD4/CD8 cells by FACS (exploratory endpoint)	Target engagement Samples will be taken only from patients receiving monotherapy

FACS=fluorescence-activated cell sorting; FOXP3=forkhead box; GM-CSF=granulocyte-macrophage colony-stimulating factor; ICF=informed consent form; ICOS=inducible T cell costimulatory; IFNγ=interferon gamma; IHC=immunohistochemistry; PBMC=peripheral blood mononuclear cells; PD= pharmacodynamics; PD-L1=Programmed Cell Death-Ligand 1; PGx=pharmacogenomics; PK=pharmacokinetic; TNFα=tumor necrosis factor alpha.

a On days and timepoints when biomarker and pharmacokinetic blood samples are being collected, the PK sample must be drawn first. For further details please see schedule of PK assessments in Section 6.4.2.

*b* Patients need to stay in the clinic for as long as possible (6 to 8 hours) for collection of plasma cytokine samples (see schedule of assessments in Section 6) in Phase 1: C2D1 and C3D1 in Phase 2: C1D1, C2D1 and C3D1 at pre-infusion and 6 to 8 hours post-infusion.

c At screening where a prior (archival) biopsy is available that is less than 3 months old this may be substituted for a fresh tumor biopsy

d In Phase 2 - No C1D2, but instead C1D1 +6 to 8 hours post-infusion.

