8.0 Conventions and Derivations

8.1 Baseline Values

Baseline is defined as the last measurement prior to first study drug administration.

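### Archival screening tissue can pre-date another anti-cancer therapy, so the tumor-biomarker change from baseline in SAP 10.6.3 can include that therapy's effect

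*Protocol*

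**What the plan says.** **Substitution rule.** The rule appears in four places in the protocol, each time limited only by the age of the tissue:

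- Table 6-1, footnote q (Phase 1): "Where a prior (archival) biopsy is available that is less than 3 months old this may be substituted for a fresh tumor biopsy".
- Table 6-2, footnote q (Phase 2): "Where a prior (archival) biopsy is available no older than 3 months, the archival tissue may be substituted for a fresh tumor biopsy at screening".
- Table 6-4, footnote c, in Section 6.3.1: "At screening where a prior (archival) biopsy is available that is less than 3 months old this may be substituted for a fresh tumor biopsy".
- Section 6.3.2, which repeats the rule and schedules the on-treatment biopsy at C2D8.

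None of them mentions therapy given after the sample, and none states the date from which the 3 months are counted.

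**Washout.** Protocol Section 4.3 excludes TKI or chemotherapy in the 2 weeks before first dose (4 weeks for cytotoxics with major delayed toxicity), and separately "Anti-CTLA4, anti-PD-(L)1 treatment within 4 weeks of the first dose of study treatment".

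**Analysis.** SAP 8.1: "Baseline is defined as the last measurement prior to first study drug administration". SAP 7.2.8 admits to the biomarker set any dosed patient with at least one ICOS, FOXP3 or CD8 result. SAP 10.6.3 then summarises change in ICOS+FOXP3+ density, CD8 density and their ratios for that set. The source of the baseline tissue plays no part. SAP 10.5.2.3 and 10.5.2.4 plan no sensitivity or supplementary analyses.

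**Use.** Change from baseline in tumor biomarkers is a secondary objective (protocol 2.1.2, SAP 5.2). On dose selection, protocol 6.3.1 adds that "it is proposed to use PD readouts to contribute to the process of RP2D decision".

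**The concern.** A change from baseline is meant to describe what happened to the tumor between the start of KY1044 and C2D8. That reading needs baseline tissue that reflects the tumor as it stood at about the first dose. If another systemic therapy was given after the archival sample was taken, the baseline shows the tumor before that therapy. The reported change then has two parts: whatever the earlier therapy did to the infiltrate, and whatever study treatment did.

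Nothing in the SAP separates the two. The earlier therapy's part could add to an apparent KY1044 effect or hide one. The readouts are one input to the RP2D, and the groups in which they are summarised are small, so a few such pairs can matter.

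**Working it through.** The plan states no figure on this point that could be reproduced. The check is date arithmetic plus a decomposition of the reported change.

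**Inputs**

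- Maximum age of archival tissue: 3 months (Tables 6-1, 6-2 and 6-4; Section 6.3.2). At 30.4375 days per month, the SAP's own conversion (SAP 8.6), this is 3 × 30.4375 = 91.3 days.
- Washout: 14 days for chemotherapy or TKI, 28 days for anti-CTLA4 or anti-PD-(L)1 (Section 4.3).
- Screening period: up to 28 days (Section 6.1.2).
- C2D8: Cycle 2 starts on study Day 22, so C2D8 is Day 22 + 7 = 29, which is 28 days after first dose.

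**Step 1. Room for another therapy between baseline tissue and first dose** (tissue age minus washout)

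| 3 months counted back from | Tissue-to-first-dose gap | Chemotherapy or TKI | Anti-CTLA4 or anti-PD-(L)1 |
|---|---|---|---|
| First dose | 91.3 days | 91.3 − 14 = 77.3 days (about 11 weeks) | 91.3 − 28 = 63.3 days (about 9 weeks) |
| Start of a full 28-day screening period | 91.3 + 28 = 119.3 days | 119.3 − 14 = 105.3 days | 119.3 − 28 = 91.3 days |

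Both rows are shown because the reference date is not stated. The first is the more conservative, and the conclusion uses it. The documents give no schedule for prior therapies, so these windows are not converted into numbers of doses.

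**Step 2. Compare with the interval of interest.** SAP 10.6.3 names no timepoint, but C2D8 is the only scheduled on-treatment biopsy. It comes 28 days after first dose.

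- Archival baseline to C2D8: up to 91.3 + 28 = 119.3 days, or 119.3 + 28 = 147.3 days on the second reading.
- Fresh screening biopsy to C2D8: at most 28 + 28 = 56 days.

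An intervening therapy can therefore have had longer to act than study treatment.

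**Step 3. What the summary would contain.** For one patient, with M the marker value:

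M(C2D8) − M(archival) = [M(C2D8) − M(first dose)] + [M(first dose) − M(archival)]

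The first bracket is the change sought. The second includes the effect of any therapy given in the Step 1 window. If a fraction f of pairs is affected and the average second bracket in those pairs is d, the group mean shifts by f × d.

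**Step 4. Scale in the planned groups.** Neither f nor d is in the documents. As an illustration only, take the dose-assessment groups in Section 3.1.4:

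- one affected pair among 5 pre-treated patients: f = 1/5 = 20%;
- two among 5: f = 2/5 = 40%;
- one among 15 naive patients: f = 1/15 = 6.7%.

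If the share were 10% to 30% (an assumption), the mean would shift by 10% to 30% of d.

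**The case against.** **The affected case needs several things together.** There must be archival tissue under 3 months old, another therapy given after it, a completed washout and a paired C2D8 sample. Fresh biopsy is the default under Section 6.3.2, and affected pairs could be traced: Section 6.3.2.2 asks that previous treatment be indicated for archival samples, and SAP 10.2 lists prior anti-cancer therapy. The analysis is descriptive, and PD readouts are only one part of the RP2D composite in Section 5.4.7. All of this stands, and it limits the weight of the point. It does not remove it, because the SAP makes no use of the traceable information.

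**Stronger readings a reader might infer, which the documents do not support:**

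- *That the protocol shows checkpoint therapy alters these endpoints.* Section 1.2 says only that "blockage of CTLA-4 with ipilimumab has been shown to induce ICOS expression on Th1 CD4 T cells". It concerns one anti-CTLA4 antibody and Th1 CD4 cells. It does not cover anti-PD-(L)1, chemotherapy or TKIs, nor the ICOS+FOXP3+ and CD8 counts in SAP 10.6.3.
- *That the problem sits mainly in anti-PD-(L)1 pre-treated patients.* The chemotherapy/TKI window is the longer one (77 against 63 days) and is open to naive patients as well.
- *That dose-level comparisons are distorted.* Nothing links use of archival tissue to dose. Chance imbalance is possible in small groups, but no systematic mechanism is described.

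**Limits of any remedy.** Tissue taken just after the last dose of an earlier drug can still carry that drug's effect, and a fresh biopsy early in screening has the same weakness. In the combination arm the change reflects KY1044 plus atezolizumab in any case. Restricting the pairs also shrinks small groups and may select against patients who recently failed a therapy. These are good reasons to keep the all-pairs summary in view.

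**Conclusion.** The point holds as a gap in the biomarker analysis. As written, the plan lets baseline tissue pre-date up to about 11 weeks of chemotherapy or TKI, or about 9 weeks of anti-CTLA4 or anti-PD-(L)1, and reports the difference to C2D8 as change from baseline.

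This rests on counting 3 months from first dose, on the washouts in Section 4.3, and on the absence of any condition on intervening therapy. That is a permission by silence, not an explicit one. The number of patients affected, the size of the shift and its direction are all unknown. Naive or pre-treated patients may be affected.

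The consequence is confined to the tumor-biomarker objective and its contribution to the RP2D decision. ORR and DLT incidence are untouched. It is a worthwhile, inexpensive SAP improvement and not a threat to the primary analyses.

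**What to change.** Change SAP 10.6.3 only:

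1. From the biopsy date and the date of last prior systemic anti-cancer therapy, flag every pair whose screening sample pre-dates any such therapy. The 3-month rule and the washout criteria already require both dates to be known.
2. Base the main change-from-baseline summary on pairs whose screening sample was taken after the last prior systemic therapy.
3. Present the all-pairs summary alongside, and list the flagged pairs separately with the intervening therapy named.

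**Cost.** A few lines of SAP text, one derived flag and one extra summary. The main summary will hold somewhat fewer pairs. That matters in pre-treated groups that may start at five patients, which is why both summaries should be shown. SAP 4.0 provides for a final version to be approved before database lock, so the change belongs there.

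No change to the biopsy requirements is needed. Tightening the substitution footnotes would mean fresh biopsies for patients who are now spared them. It may also come too late for enrolment, since the protocol synopsis plans the end of the clinical phase for Q3 2023 / Q1 2024 and SAP version 3.0 is dated March 2024.
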